8.6.2. Covariates

For efficacy analyses, the baseline values will be used as covariates in the analysis models. Other important prognostic factors will be specified in the SAP for the study.

8.6.3. Missing Data

All data will be used as observed, and no imputations will be made for any missing data point for early phase study.

8.7 ANALYSIS METHODS

A SAP will be developed and approved before the database is locked. The SAP will present the detailed statistical methodology to be used in analyzing the data from this trial.

8.7.1. Subject Disposition

The disposition of all subjects who sign an ICF will be provided. The numbers of subjects screened, enrolled, completed, and discontinued during the study, as well as the reasons for all post-enrollment discontinuations will be listed and/or summarized by treatment group. Disposition and reason for study discontinuation will also be provided as a by-subject listing.

8.7.2. Demographic and Baseline Disease Characteristics

Demographics and baseline disease characteristics including medical history, prior and concomitant medications/therapies will be listed and/or summarized by treatment group using appropriate descriptive statistics.

8.7.3. Study Analyses

8.7.3.1 Primary Analysis

The primary analysis will be conducted on the Intent-to-treat (ITT) population.

Primary Outcome (Endpoints) Measures:

Phase Ib

- Maximum Tolerated Dose (MTD) by evaluation of dose-limiting toxicities (DLTs) of leronlimab (PRO 140) when combined with carboplatin AUC5.

Note: The MTD is defined as 1 dose level below the dose in which dose limiting toxicities (DLTs) were observed in ≥ 33% of the participants during Cycle 1.

Phase II

- Progression free survival (PFS) defined as time in months from the date of first study treatment to the date of disease progression or death from any cause, whichever comes first.

Note: All patients who receive at least one dose of leronlimab (PRO 140) and carboplatin combination will be included in the primary analyses of PFS. The Response Evaluation Criteria in Solid Tumors (RECIST v1.1) criteria will be used for objective tumor response assessment (when disease is measurable and non- measurable);

The time in months from start of treatment to progression or death will be measured for all patients who receive at least one dose of study drug. Patients will be followed up to 2 years after completion of treatment.

Secondary Outcome (Endpoints) Measures:

Phase Ib

- The number, frequency, and severity of adverse events (AEs) collected from the time of first treatment until 12 weeks after study treatment completion to evaluate safety of leronlimab (PRO 140) and carboplatin in subjects with CCR5+ mTNBC.

Note: Adverse events will follow National Cancer Institute Common Terminology Criteria for Adverse Events (CTCAE) version 5.0

Phase II

- PFS according to RECIST v1.1 in participants with Detectable Programmed Death-Ligand 1 (PD-L1)

Note: The PD-L1 expression testing will be performed at baseline. Breast tissue (primary or metastatic site) collected to analyze for the presence of CCR5 at pre-screening will additionally be used for evaluating PD-L1 expression levels.

- Overall response rate (ORR, defined as Complete Response (CR) + Partial Response (PR)), and clinical benefit rate (CBR, defined as CR + PR + Stable Disease (SD)) in subjects with CCR5+ mTNBC treated with leronlimab (PRO 140) and carboplatin.

Note: Overall response rate defined as the proportion of patients who achieve an overall response of complete response or partial response in the total number of evaluable patients, assessed by RECIST v1.1. Clinical benefit rate is defined as the proportion of patients who achieve an overall response of complete response or partial response or stable disease in the total number of evaluable patients, assessed by RECIST v1.1. Imaging scans to be done at the end of 2 cycles (i.e., every 6 weeks) for the first 6 cycles (18 weeks) and at the end of 3 cycles (i.e., every 9 weeks) thereafter.

- Time to new metastases (TTNM);

Note: Recorded time from baseline metastatic disease (at time of enrollment) to the time of development of new metastasis in different site. New metastases in same site will be also recorded.

- The change from baseline in circulating tumor cells (CTC) level in the peripheral blood.

Note: Reported unit of measure will be the number of CTCs/milliliter. CTCs enumeration will be performed at baseline and at the time of response assessment. Fraction of baseline positive and change from ≥ 5 CTCs will be recorded and reported.

- Overall survival defined as time in months from the date of first study treatment to the date of death;

Note: Patients will be followed from the start of treatment until 2 years post-treatment or death, whichever occurs first, and average survival time will be measured.

- The number, frequency, and severity of AEs collected from the time of first treatment until 12 weeks after study treatment completion to evaluate safety of leronlimab (PRO 140) and Carboplatin in subjects with CCR5+ mTNBC.

Exploratory Outcome (Endpoints) Measures:

- Measure immune biomarkers (PD-L1) in CTCs, metastatic tissue and immune cells such as CAMLs and correlate with therapeutic benefit (PFS); and

- Correlation between CCR5 expression (CTCs, CAMLs) and PD- L1 expression.

PFS will be calculated using Kaplan-Meier curves and the median PFS will be read from this curve. Response rates (overall response rate, clinical benefit rate) will be calculated using proportions and 95% confidence intervals. Time to new metastases and overall survival will also be analyzed using Kaplan-Meier curves. Exploratory serial blood markers will be related to PFS using Cox regression, and to response using logistic regression.

8.7.3.2 Safety Analyses

Safety will be assessed by close monitoring and timely assessment of adverse events (AEs), laboratory parameters (blood tests, urinalysis), vital signs (blood pressure, heart rate), subject's medical condition (physical examination including weight), general well-being and activities of daily life (Eastern Cooperative Oncology Group (ECOG) performance status). Each subject will be regularly assessed in each cycle for potential AEs and disease related signs and symptoms. The CTCAE v5.0 will be used to grade toxicities / AEs.

The Safety population will be used for the analysis of safety endpoints.

Descriptive statistics (n, mean, standard deviation, median, minimum, and maximum) will be calculated for continuous variables. Frequencies and percentages will be presented for categorical variables.

Adverse Events:

Adverse events will be coded using the most recent version of Medical Dictionary for Regulatory Activities (MedDRA). Treatment Emergent AE's (TEAE) are defined as events with an onset on or after the first treatment. TEAEs will be summarized by study phase, treatment group, System Organ Class, and preferred term. The following TEAE summaries will be provided:

- Overall (i.e., regardless of severity or relationship to treatment)
- By severity grade (mild, moderate, severe, or life threatening for SAEs)
- By relationship to clinical trial treatment according to the mapping scheme below:
 - Potentially related: will include all adverse events with a relationship rating of “definitely”, “probably” or “possibly”.
 - Unlikely/not related: will include all adverse events with a relationship rating of “unlikely” or “unrelated”.

In addition, separate summaries of serious adverse events, and adverse events resulting in discontinuation of study treatment will be presented.

Clinical Laboratory Data

All laboratory values will be listed. Laboratory measurements will also be summarized as continuous variable and presented by treatment group and time point.

Physical Examination

All physical examination findings will be listed and/or summarized.

Vital Signs

All vital sign findings will be listed and summarized.

Electrocardiograms (ECGs)

All ECG findings will be listed and summarized.

Eastern Cooperative Oncology Group (ECOG) performance status

All ECOG performance status findings will be listed and summarized.

9 ADVERSE EVENTS (DEFINITIONS AND REPORTING)

The Investigator is responsible for the detection and documentation of events meeting the criteria and definition of an AE or SAE, as provided in this protocol. During the study when there is a safety evaluation, the Investigator or site staff will be responsible for detecting, documenting and reporting AEs and SAEs as detailed in this Section of the protocol.

9.1 ADVERSE EVENT (AE)

An adverse event (AE) is defined as any unfavorable or unintended sign, symptom, or disease that occurs or is reported by the subject to have occurred, or a worsening of a pre-existing condition. An adverse event may or may not be related to the study treatment.

AEs will be elicited through direct questioning and subject reports. Any abnormalities in visit evaluations, physical examination findings or laboratory results that the investigator believes are clinically significant to the research subject and that occurred after initiation of the first study treatment will be reported as AEs. Abnormal findings that are NOT clinically significant should be not be recorded as an AE

9.2 REPORTING AND FOLLOW-UP OF ADVERSE EVENTS

Report initiation for all AEs and serious adverse events (SAEs), (see [Section 9.3](#)), will begin at the time of the first treatment and continue up to the final study visit. All events will be followed to resolution or until 30 days after the subject completes the study. A final assessment of outcome will be made at that time.

All AEs must be recorded in the subject's medical records and on the CRF. AEs will be reported using customary medical terminology along with the following information: the onset and end dates, whether the event is considered to be a SAE (see [Section 9.3](#)), the impact the event had on study treatment (see [Section 9.2.1](#)), the CTCAE grade (intensity) of the event (see [Section 9.2.2](#)), the causality of the event (see [Section 9.2.3](#)), whether treatment was given as a result of the event (see [Section 9.2.4](#)), and the outcome of the event (see [Section 9.2.5](#)).

9.2.1. Impact on Study Treatment

The impact the event had on the study treatment will be assessed as either: none, study treatment interrupted, study treatment discontinued, or not applicable. The “not applicable” assessment will be used only when the subject is no longer in the treatment period of the protocol or died.

9.2.2. CTCAE Grade (Intensity) Assessment

The guidelines outlined in CTCAE v5.0 will be used for assessing the intensity of the event. The general guidelines for assessing the AE grade appear below. Full guidelines may be obtained at

https://ctep.cancer.gov/protocolDevelopment/electronic_applications/docs/CTCAE_v5_Quick_Reference_5x7.pdf

Table 9-1: CTCAE v5.0 General Guidelines

Grade	Description
Grade 1	Mild; asymptomatic or mild symptoms; clinical or diagnostic observations only; intervention not indicated.
Grade 2	Moderate; minimal, local or noninvasive intervention indicated; limiting age-appropriate instrumental activities of daily living (ADL)*.
Grade 3	Severe or medically significant but not immediately life-threatening; hospitalization or prolongation of hospitalization indicated; disabling; limiting self care ADL†.
Grade 4	Life-threatening consequences; urgent intervention indicated.
Grade 5	Death related to AE.‡

*Instrumental ADL refer to preparing meals, shopping for groceries or clothes, using the telephone, managing money, etc.

†Self care ADL refer to bathing, dressing and undressing, feeding self, using the toilet, taking medications, and not bedridden.

‡Unlike the AE outcome assessment (see [Section 9.2.5](#)), a subject may have more than one Grade 5 event.

Common Terminology Criteria for Adverse Events (CTCAE), v5.0: Nov 27, 2017

9.2.3. Causality Assessment

Adverse events will be assigned a relationship (causality) to the study treatment. The Investigator will be responsible for determining the relationship between an AE and the study treatment. The type of event, organ system affected, and timing of onset of the event will be factors in assessing the likelihood that an AE is related to the study treatment. Relationship of AEs to study treatment will be classified as follows:

- 1. Unrelated** – The event is definitely not associated with the study biologic or control. Other conditions including concurrent illness, progression or expression of the disease state, or reaction to a concurrent medication explain the reported AE.
- 2. Unlikely** – The temporal association, patient history and/or circumstances are such that the study biologic or control is not likely to have had an association with the observed event. Other conditions including concurrent illness, progression or expression of the disease state, or reaction to a concurrent medication, appear to explain the reported AE.
- 3. Possibly** – The event follows a reasonable temporal sequence from study biologic or control but could have been produced by the patient's clinical state or other therapies administered to the patient.
- 4. Probably** – The event follows a reasonable temporal sequence from the study biologic or control, abates upon discontinuation of the study drug or control, or cannot be reasonably explained by known characteristics of the patient's clinical state.

5. Definitely – The event follows a reasonable temporal sequence from the study biologic or control, abates upon discontinuation and cannot be explained by known characteristics of the patient’s clinical state.

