- d. The occurrence in any subject of a life-threatening SAE whose causal relationship to leronlimab (PRO 140) is judged to be probable or definite
- e. The occurrence of one or more non-life-threatening SAEs whose causal relationship to leronlimab (PRO 140) is judged to be definite
- f. The occurrence, in one or more subjects, of Grade 4 laboratory abnormalities, judged to be probably or definitely related to receipt of leronlimab (PRO 140)
- g. The occurrence of hematologic and non-hematological adverse events, judged to be possibly, probably or definitely related to receipt of leronlimab (PRO 140) based on previous clinical experience and that are of CTCAE Grade 3 or greater severity. Permissible exceptions to this rule include Grade 3 fatigue of less than one week duration, and Grade 3 nausea, vomiting, and diarrhea that resolve within 48 hours following institution of appropriate supportive care.
- h. Hy's law
- i. Neutropenic fever
- j. Grade 4+ neutropenia or thrombocytopenia >7 days
- k. Grade 3+ thrombocytopenia with bleeding
- l. Grade 3+ electrolyte abnormality that lasts >72 hours, unless the patient has clinical symptoms, in which case all grade 3+ electrolyte abnormality regardless of duration should count as a DLT. Grade 3+ amylase or lipase elevation NOT associated with symptoms or clinical manifestations of pancreatitis does not need to be counted as a DLT
- m. For patients with hepatic metastases, AST or ALT >8xULN or AST or ALT >5x ULN for ≥ 14 days

If any of the SAEs or DLTs outlined above have occurred, the Data Safety Monitoring Board (DSMB) will conduct an independent review of the data and make a final decision for dose escalation to the next cohort.

The dosing regimen for each cohort is as follows:

- Cohort A: 350 mg leronlimab (PRO 140) SC weekly + AUC 5 Carboplatin every 3 weeks
- Cohort B: 525 mg leronlimab (PRO 140) SC weekly + AUC 5 Carboplatin every 3 weeks
- Cohort C: 700 mg leronlimab (PRO 140) SC weekly + AUC 5 Carboplatin every 3 weeks

Leronlimab (PRO 140) is administered as subcutaneous injection in the abdomen weekly. A total of 350 mg, 525 mg, or 700 mg (175 mg/mL) is delivered as two injections on opposite sides of the abdomen. The 350 mg dose will be delivered as two injections of 1 mL each, 525 mg dose will be delivered as two injections of 1.5 mL each and 700 mg dose will be delivered as two injections of 2 mL each.

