6 STUDY TREATMENT

Eligible subjects will receive the combination leronlimab (PRO 140) and carboplatin. Leronlimab (PRO 140) will be administered weekly at a dose assigned at time of enrollment and carboplatin target of AUC 5 every 3 weeks as combination therapy until disease progression or intolerable toxicity.

Table 6-1: Treatment Administration Summary

Study Drug	Premedication	Dose	Route	Schedule	Cycle Length	Supportive Therapies
Leronlimab (PRO 140)	N/A	Assigned dose cohort*	SC	Start on Day 1 and every week thereafter	N/A	N/A
Carboplatin	Antiemetics	AUC 5	IV Infusion	Day 1 every 3 weeks (21 Days)	3 weeks (21 Days)	Omeprazole or similar agents, ondansetron or similar antiemetics

*Phase Ib: Cohort A: 350 mg PRO 140 SC weekly; Cohort B: 525 mg PRO 140 SC weekly; Cohort C: 700 mg PRO 140 SC weekly

*Phase II: MTD PRO 140 SC weekly

Supportive care: Any required supportive care treatment such as antibiotics, anti- emetics, proton pump inhibitors and others will be given per institutional standards.

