8.4.1 Adverse Events

Adverse events will be classified by system organ class (SOC) and preferred term (PT) according to the most recent version of MedDRA dictionary.

TEAE are defined as adverse events with onset date on or after the first treatment. TEAEs will be summarized by treatment group, System Organ Class, and preferred term. The following TEAE summaries will be provided:

- a) Overall (i.e., regardless of severity or relationship to treatment)
- b) By severity grade
- c) By relationship to clinical trial treatment

Unless otherwise specified, at each level of subject summarization, a subject will be counted only once. If there is more than one occurrence of an event, the event of the worst severity or the worst-case relationship category will be summarized.

AEs leading to premature discontinuation of clinical trial treatment and Serious Adverse Events (SAEs) will also be summarized by treatment group and relationship.

All adverse events recorded in the eCRF will be presented as by-subject listings.

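### The single AE causality rating does not say whether it refers to leronlimab or to the leronlimab–carboplatin combination, and the single AE action code has the same gap and no dose-reduction option

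*Protocol*

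**What the plan says.** **Causality.** Protocol Section 9.2 lists what is recorded for each event, and relationship appears there once, as "the causality of the event". Section 9.2.3 opens: "Adverse events will be assigned a relationship (causality) to the study treatment". Section 6, headed Study Treatment, states: "Eligible subjects will receive the combination leronlimab (PRO 140) and carboplatin". The five categories in 9.2.3 do not use that term. Each is written against the study biologic or control. *Unrelated* begins "The event is definitely not associated with the study biologic or control" and offers as one alternative explanation a "reaction to a concurrent medication explain the reported AE".

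**Action taken.** Section 9.2.1 gives one closed list: "The impact the event had on the study treatment will be assessed as either: none, study treatment interrupted, study treatment discontinued, or not applicable".

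**Use of the rating.** Protocol Section 8.7.3.2 collapses it into two classes, potentially related (*Possibly* and above) and unlikely/not related. SAP 8.4.1 plans a TEAE summary "By relationship to clinical trial treatment", and summarizes SAEs and AEs leading to treatment discontinuation by relationship as well. Neither document splits relationship by drug. Section 12 includes related AEs in what the DSMB reviews.

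**Rules that name leronlimab.** Several DLT items in Section 3 depend on attribution to leronlimab itself. Item g, for example, covers events "judged to be possibly, probably or definitely related to receipt of leronlimab (PRO 140) based on previous clinical experience". Section 6.1.5 permanently stops leronlimab when an AE related to leronlimab requires a hold of more than 21 days.

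**The concern.** The lead sentence of 9.2.3 and its categories point to different objects, and nothing elsewhere settles which is meant. There is no control arm: Phase Ib escalates the combination and Phase II is single arm. Carboplatin is not a biologic. Section 6.2.9 calls it standard of care, which invites an investigator to treat it as a concurrent medication. The term study treatment is not used consistently either: Section 4 says it may be self-administered at home, which cannot describe intravenous carboplatin.

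Safety of the combination is a Phase Ib primary objective and a Phase II secondary objective. A related-AE table whose object varies by center cannot say what it is counting. Section 9.2.1 adds to this: a reduction of either drug has no code, and the discontinuation summary does not say which drug was stopped.

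**Working it through.** No sample-size or power arithmetic applies. The check is a comparison of the text under two readings, plus one count.

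**1. Two readings of the single rating**

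| | Reading A: leronlimab alone | Reading B: the combination |
|---|---|---|
| Support | Category wording in 9.2.3; the home-administration use in Section 4; standard-of-care status in 6.2.9 | Lead text of 9.2.3; Section 6; safety endpoint in 8.7.3.1, which names both drugs |
| Clear carboplatin toxicity | Can be rated *Unrelated* or *Unlikely*, and so fall in the not-related class | Rated as related |
| Leronlimab-specific attribution | Supplied by the rating | No defined field |
| What is lost | Carboplatin toxicity in by-relationship tables, and among the related AEs sent to the DSMB | A recorded basis for the DLT items and hold rule that name leronlimab |

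Each reading loses something, but not the same thing.

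**2. Example: thrombocytopenia after carboplatin.** Section 6.2.10 lists it as carboplatin's dose-limiting effect. Sections 1.3.2 and 1.5 tell investigators to expect no marrow overlap and no major toxicity overlap with leronlimab. Under A, that background supports *Unrelated* or *Unlikely*. Under B, the same event is potentially related. Section 3.1 allows up to five centers, and the analysis dataset would not show which reading produced a given record.

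**3. Count of DLT items (Section 3, a to m)**

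- Graded relationship to leronlimab required: a, d, e, f, g = 5.
- Names leronlimab as cause without a graded term: b = 1.
- Turns on the injection-site reaction itself: c = 1.
- No attribution test: h, i, j, k, l, m = 6.
- Total: 5 + 1 + 1 + 6 = 13.

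So 5 of 13 items (6 if b is included) need a leronlimab-specific judgement, as does the hold rule in 6.1.5.

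**4. Action codes against permitted actions**

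| Action the protocol allows | Where | Code in 9.2.1 |
|---|---|---|
| Leronlimab dose reduced | 6.1.5 | None fits |
| Carboplatin dose reduced | 6.2.13, Table 6-4 and following text | None fits |
| Carboplatin stopped, leronlimab continued | 6.2.13, note to Table 6-4 | Discontinued or not, depending on the reader |

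**The case against.** The strongest reply is that little depends on this field.

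- **DLTs are not derived from it.** Under Section 3 the PI determines directly whether a listed event occurred, the sponsor's medical monitor reviews safety data before escalation, and the DSMB reviews independently if a listed event occurs. This stands. A reader might infer that five DLT items fail, or that the DSMB cannot check attribution. The documents do not show that: the DLT text itself calls for the leronlimab judgement, and the CRF and DSMB charter are not among them. What can be said is that neither the protocol nor the SAP defines a field for it.
- **Carboplatin toxicity is not simply classed as unrelated.** A reader might infer that it is. But the lead text refers to study treatment, *Possibly* covers well-timed events that other therapies could have caused, and *Possibly* counts as potentially related. The supportable word is *can*. Nor would a center using Reading B necessarily choose *Definitely*, since that category requires the event to abate on discontinuation.
- **The two losses are alternatives.** A reader might infer that one rating both hides carboplatin toxicity and lacks leronlimab attribution. For any single rating they exclude each other. Both can appear in one dataset only if centers differ.
- **The safety endpoint is the number, frequency and severity of AEs.** TEAEs are tabulated overall regardless of relationship, and all AEs are listed by subject, so the toxicity remains visible. The DSMB also receives unexpected AEs, SAEs and deaths, so serious carboplatin events reach it by another route. This stands and limits the effect.
- **Dose reductions are not lost.** SAP 8.1.5 lists and summarizes drug administration. What is missing is the code linking a reduction to the event that caused it.

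After these concessions, what remains is a rating scale that does not fit the trial and still feeds planned tables, and a closed action list that omits actions the protocol permits.

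**Conclusion.** The point holds as an ambiguity. Depending on the reading, either the by-relationship tables can understate carboplatin toxicity, or the leronlimab judgement in 5 of 13 DLT items and the 21-day hold rule has no defined place in the protocol or SAP. If centers differ, the pooled by-relationship summaries cannot be interpreted. The action field separately has no code for a reduction of either drug and cannot show which drug was stopped.

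The number of misclassified events cannot be estimated from the documents. Planned enrolment of up to 18 + 30 = 48 patients is the population exposed to the problem, not a measure of its size. The overall TEAE tables, the PFS analysis and the six DLT items without an attribution test are unaffected. The conclusion assumes that the CRF follows the protocol text; a CRF that already has per-drug causality and action fields would largely remove the problem, leaving protocol and SAP wording to align.

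**What to change.** - **Protocol 9.2.3:** replace the reference to the study biologic or control. Rate causality separately to leronlimab and to carboplatin on the same five-point scale, and state that carboplatin is not a concurrent medication for this purpose.
- **Protocol 9.2.1:** record action taken separately for each drug and add a dose-reduced option.
- **Protocol 8.7.3.2 and SAP 8.4.1:** tabulate TEAEs related to leronlimab, to carboplatin and to either, and present discontinuations by drug.

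The cost is a few extra AE form fields, amendment and SAP wording, some additional safety tables, and two attributions per event for investigators. No dose, DLT threshold or clinical rule changes. Per-drug attribution is hard to reconstruct reliably afterwards, so it should be collected as events are reported.
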